2.1. Primary Objective

The primary objective of the study is:

- To evaluate the safety and tolerability of NTZ 500mg bid after 24 weeks of treatment in patients with NASH induced Stage 2 or Stage 3 fibrosis.

2.2. Secondary Objectives:

The secondary objectives of the study are:

- To determine the effect of daily oral administration of NTZ 500mg bid on de novo collagen synthesis through Fractional Synthesis Rate (FSR) of circulating plasma proteins in patients with NASH-induced Stage 2 or Stage 3 fibrosis.
- To evaluate changes in liver stiffness as measured by FibroScan® and by Magnetic Resonance Elastography (MRE).
- To assess the change from baseline in non-invasive markers of fibrosis: ELF™ test score, PIIINP, Hyaluronic acid, CK18, TIMP-1, YKL-40, Alpha 2 macroglobulin,, ,miRNA, ProC3, ProC6, FGF19, FGF21.
- To assess changes in additional non-invasive tests: fibrosis scores: NAFLD fibrosis score, FIB-4

3. Study Design

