6.6.3. Dose Adjustment

Enrolled subjects who experience treatment emergent adverse events should be monitored closely and may have the NTZ dose adjusted at the Principal Investigator's discretion.

Enrolled subjects who experience a possible treatment emergent adverse event will be assessed for symptoms and further biochemical assessments as follows:

- GI Adverse Events: the subject will be assessed for abdominal pain, loss of appetite, nausea and vomiting. Blood will be collected for amylase and lipase assessment to rule out pancreatitis.
- Kidney Function Adverse Events: the subject will have blood samples collected for eGFR to rule out kidney dysfunction.
- Musculoskeletal Adverse Events: the subject will be assessed for fatigue, muscle aches and pain. Blood samples will be collected for Creatine Kinase.

The following procedure will be followed for dose adjustments:

1. Patients will be asked to hold drug for 3 days
2. After the 3-day drug hold, patients will be reassessed for adverse event symptoms.
 - If the AE symptoms have resolved following 3 days of drug hold, the patient will discontinue NTZ dosing permanently and will be followed per the schedule of assessments.

If the AE symptoms have not resolved following 3 days of drug hold, the patient will be restarted on a reduced dose of 500 mg NTZ, once a day for 7 days. Patients will be evaluated for treatment emergent adverse events and consideration for resuming the dosage of 500mg NTZ twice a day. PI may determine that the patient should remain at the 500 mg NTZ once a day dose following 7 days of reduced dose. In such scenarios, the patient will be monitored and consideration for resuming the dosage of 500 mg NTZ twice daily will be evaluated at each subsequent visit.

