7.2.3. Action taken and outcome

The Investigator will record the action taken with drug and outcome of the event for each AE according to the following:

Action taken with investigational drug

- Drug permanently withdrawn – in case a patient is permanently withdrawn from the study drug
- Drug temporarily withdrawn – in case the study drug is temporarily withdrawn
- Dose not changed – in case no action is taken regarding the study drug
- Unknown
- Not applicable – an AE started before initiation of treatment with study drug, the treatment had been completed prior to reaction/event, or the patient has died.

Outcome

- Recovered/resolved

- Recovering/resolving
- Not recovered/not resolved
- Recovered/resolved with sequelae
- Fatal
- Unknown.

Note: In case of irreversible congenital anomalies the choice not recovered/not resolved should be used. “Fatal” should be used when death is possibly related to the reaction/event.

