2 STUDY OVERVIEW

2.1 Study Objectives and Endpoints

Primary	
Objective	Endpoint
To evaluate the safety and tolerability of NTZ 500 mg twice daily (BID) after 24 weeks of treatment in patients with non alcoholic steatohepatitis (NASH)-induced stage 2 or stage 3 fibrosis.	Adverse events (AEs) including treatment-emergent AEs (TEAEs) and serious AEs (SAEs), laboratory evaluations, vital signs, electrocardiograms (ECGs), and physical examinations.
Secondary	
Objective	Endpoint
To determine the effect of oral administration of NTZ 500 mg BID on de novo collagen synthesis through Fractional Synthesis Rate (FSR) of circulating plasma proteins in patients with NASH induced stage 2 or stage 3 fibrosis.	Percent change in FSR from baseline to end of treatment (24 weeks of treatment).
To assess changes in liver stiffness as measured by FibroScan® and by Magnetic Resonance Elastography (MRE).	Observed change in liver stiffness by FibroScan from baseline to 24 weeks of treatment Observed change in liver stiffness by MRE from baseline to 12 weeks and 24 weeks of treatment.
To assess the change from baseline in non-invasive markers of fibrosis: ELF™ test score, PIIINP, Hyaluronic acid, CK18, TIMP-1, YKL-40, Alpha 2 macroglobulin, miRNA, ProC3, ProC6, FGF19, and FGF21.	Observed change in non-invasive biomarkers of fibrosis from baseline to 12 weeks and 24 weeks of treatment.
To assess changes in additional non-invasive tests: fibrosis scores: non alcoholic fatty liver disease (NAFLD) fibrosis score and FIB-4.	Observed change in fibrosis scores from baseline to 12 weeks and 24 weeks of treatment.

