3.3.6 Study Drug Exposure and Compliance

Days of exposure to study drug will be calculated as date of last dose of study drug as recorded on the end of study form – date of first dose of study drug + 1. Note that the exposure calculation is intended to describe the length of time a subject was exposed to study drug and therefore does not take study drug interruptions into account. Days of exposure to study drug will be summarized based on the Safety Analysis Set with descriptive statistics and with counts and percentages of subjects with exposure in the following categories:

- <4 weeks (<29 days)
- 4 to <8 weeks (29 – 56 days)
- 8 to <12 weeks (57 – 84 days)
- 12 to <16 weeks (85 – 112 days)
- 16 to <20 weeks (113 – 140 days)
- 20 to <24 weeks (141 – 168 days)
- ≥24 weeks (≥169 days)

Percent compliance to the study drug regimen will be calculated as $100 \times \text{number of actual capsules taken} / \text{number of expected capsules taken}$. The number of actual capsules taken will be calculated as number of capsules dispensed – number of capsules returned. If study drug is not returned, the number of capsules returned will be considered 0 for the compliance calculation, i.e. it will be assumed that the subject took all capsules. The number of capsules expected will be calculated as $2 \times \text{days of exposure}$. Percent compliance to the study drug regimen will be summarized based on the Safety Analysis Set with descriptive statistics and with counts and percentages of subjects with compliance in the following categories:

- <80%
- 80-120%
- >120%

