3.5 Safety Assessments

3.5.1 Adverse Events

All AEs regardless of seriousness or relationship to study drug, including those occurring during the Screening Period, are to be recorded on the corresponding page(s) of the CRF and in the patient's medical record from the informed consent form signature until study end for each patient. All AEs will be coded to system organ class and preferred term using Medical Dictionary for Regulatory Activities (MedDRA) version 21.0.

TEAEs are defined as AEs that worsen in severity or relationship to study drug or commence on or after the time of start of first study drug administration. This may include AEs that start during follow-up after the last dose of study drug.

Study drug related AEs are defined as AEs that are possibly related or related.

An overview of AEs based on the Safety Analysis Set will be provided including counts and percentages of subjects with the following:

- Any TEAEs (overall and by maximum severity)
- Any study drug related TEAEs (overall and by maximum severity)
- Any SAEs
- Any study drug related SAEs
- Any deaths due to AEs
- Any AEs leading to withdrawal from study or study drug
- Any study drug related AEs leading to withdrawal from study or study drug

Counts and percentages of subjects will also be presented by system organ class and preferred term for TEAEs and study drug related TEAEs. In addition, summaries will be provided by system organ class, preferred term, and maximum severity.

Listings will be presented specifically for SAEs and TEAEs leading to withdrawal from study or study drug.

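### AE-driven reductions to 500 mg once daily have no action-taken code and no summary row, so no planned table shows how many patients stayed on the BID regimen named in the primary objective

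*SAP*

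**What the plan says.** Protocol 2.1 sets the primary objective: "To evaluate the safety and tolerability of NTZ 500mg bid after 24 weeks of treatment". SAP 2.1 repeats it and gives the endpoint as "Adverse events (AEs) including treatment-emergent AEs (TEAEs) and serious AEs (SAEs), laboratory evaluations, vital signs, electrocardiograms (ECGs), and physical examinations". Dose modification is not a component.

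Protocol 6.6.3 provides for AE-driven changes of dose. After a 3-day hold, one branch is that "the patient will be restarted on a reduced dose of 500 mg NTZ, once a day for 7 days". This can be extended: "PI may determine that the patient should remain at the 500 mg NTZ once a day dose following 7 days of reduced dose". A return to BID is then reconsidered at each later visit, with no outer limit.

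For each AE, Protocol 7.2.3 has the investigator record one of five actions: permanently withdrawn, temporarily withdrawn, unchanged, unknown, or not applicable. The unchanged entry reads "Dose not changed – in case no action is taken regarding the study drug". No entry stands for a reduced dose.

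On the analysis side, Protocol 8.5.1 summarises TEAEs leading to discontinuation of study drug. The SAP 3.5.1 overview has "Any AEs leading to withdrawal from study or study drug" and the same row restricted to drug-related AEs; its dedicated listings cover SAEs and TEAEs leading to withdrawal. SAP 3.3.6 measures exposure from first to last dose and says that this "does not take study drug interruptions into account". Compliance is tablets taken divided by twice the days of exposure, whatever dose was prescribed, and unreturned drug is treated as taken.

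**The concern.** The objective names a regimen, not only a drug. In a single-arm study of 20 patients, a reader will want to know how many were still taking 500 mg twice daily at Week 24, and how many were moved off it because of an AE.

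The protocol creates a third outcome between staying on BID and stopping, but gives the site no accurate way to code it. The nearest choices are temporary withdrawal, which describes the hold but not the lower dose that follows; dose unchanged, which would be untrue; or unknown. The planned tables then count only withdrawals. A patient who spent weeks on half the daily dose because of an AE would show close to 24 weeks of exposure, and the AE tables would not say that the dose had been cut.

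**Working it through.** The plan has no figure to reproduce: the sample size of 20 rests on clinical assessment, and no rate of dose reduction is given. Two checks were made.

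**1. Does the compliance table in SAP 3.3.6 reveal reductions?**

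Inputs: treatment length T = 168 days (169 if both end days count); expected tablets 2T = 336 (338); a 3-day hold misses 6 tablets; each once-daily day misses 1. Assume that the patient otherwise takes every tablet and returns all unused drug. With q once-daily days:

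compliance = 100 × (2T − 6 − q) / 2T

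- Hold plus 7 once-daily days, then BID again: 323/336 = 96.1% (325/338 = 96.2%). This is in the 80–120% band.
- Reduction kept to the end of treatment: compliance is at least 80% when q ≤ 0.4T − 6, which is 61.2 for T = 168 and 61.6 for T = 169, so up to 61 days. At q = 61 it is 269/336 = 80.1% (80.2% for T = 169). At q = 62 it is 268/336 = 79.8% (79.9%). A hold beginning on about Day 105 or 106, or later, therefore leaves the patient in the 80–120% band.
- Longer reductions do fall below 80%: q = 84 gives 73.2–73.4%, and q = 112 gives 64.9–65.1%. BID for 14 days, a 3-day hold, then once daily for 151 days gives 28 + 151 = 179 tablets, and 179/336 = 53.3%. These patients are visible, but the table cannot distinguish a directed reduction from missed doses.
- Unreturned drug can hide even a long reduction. Protocol 5.2 gives 6 × 12 = 72 tablets per 4-week box. A once-daily patient uses 28 in that period, so an unreturned box credits 72 − 28 = 44 tablets that were not taken.

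**2. How much could the missing row matter?**

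Each patient is 1/20 = 5 percentage points. The number of reductions is assumed to be 1 to 4 of 20, with no permanent withdrawals, and exact (Clopper-Pearson) 95% intervals are used.

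| Patients reduced because of an AE | Permanent-withdrawal row | Not kept on BID because of an AE |
|---|---|---|
| 1 | 0/20 = 0% (0–16.8%) | 5% (0.1–24.9%) |
| 2 | 0/20 = 0% (0–16.8%) | 10% (1.2–31.7%) |
| 3 | 0/20 = 0% (0–16.8%) | 15% (3.2–37.9%) |
| 4 | 0/20 = 0% (0–16.8%) | 20% (5.7–43.7%) |

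The chance that at least one of 20 patients is reduced is 1 − (1 − p)^20: 64%, 88%, 96% and 99% for true rates p of 5%, 10%, 15% and 20%. Unless reductions are rare, the situation is likely to arise.

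**The case against.** A reader might infer that these patients drop out of the primary result, or that a tolerability rate is biased downward. The documents do not support either reading. Protocol 8.5 assesses tolerability through AEs, laboratory tests, vital signs, ECGs and physical examinations. The AE behind a reduction enters the any-TEAE row, the severity and SOC/preferred-term tables and, if judged so, the drug-related rows. The plan defines no rate of remaining on BID, so no planned estimate is biased. What is missing is a summary of the action taken.

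Four further points stand in part:

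- **Compliance.** Long reductions show up below 80%. Shorter ones do not, and no reason is attached to any of them.
- **The word withdrawal.** Protocol 7.2.3 uses it for both permanent and temporary stops, and every reduction follows a hold. If temporary withdrawals were counted in the SAP row, reduced patients would appear there, mixed with those who stopped for good. Protocol 8.5.1, which speaks of discontinuation, favours the permanent reading, but the SAP does not settle it.
- **Other records.** Protocol 5.5 has the duration and reason of interruptions documented, Protocol 9.6 keeps the dose regimen in source, and SAP 7 lists all available data. The eCRF is not among the documents, so a dosing form may record reductions. A listing is still not a summary, and the AE action field still lacks the code. Protocol 7.1.2 does name drug interruption and modification, but only for laboratory abnormalities, so it does not fill the gap for AEs in general.
- **Who is reduced.** As written, Protocol 6.6.3 sends patients whose symptoms resolve on hold to permanent discontinuation, so they are counted, and restarts at the lower dose those whose symptoms persist. It would therefore go too far to describe every reduced patient as unable to tolerate BID dosing.

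**Conclusion.** The concern holds as a reporting gap on the primary objective. The plan permits an open-ended, AE-driven reduction to once daily, has no action code that records it accurately, and summarises only discontinuation or withdrawal, with the latter undefined. As a result, no planned summary shows how many patients left 500 mg BID because of an AE, and the compliance table does not reliably supply that count.

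The size is 5 percentage points per patient, or 5 to 20 points under the assumed 1 to 4 reductions in 20. That range is an assumption, as is the absence of permanent withdrawals in the table. The compliance results assume full adherence to the prescribed dose and full return of unused drug. The gap affects how tolerability of the regimen is described; it does not remove any adverse event from the analysis.

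**What to change.** 1. **Protocol 7.2.3 and eCRF:** add a dose-reduced entry to the action-taken list, preferably while AE data are still being collected. For events already entered, the regimen in source documents should allow recoding.
2. **SAP 3.5.1:** define withdrawal from study drug as permanent. Add separate rows for TEAEs leading to interruption, to dose reduction and to permanent withdrawal, and one row for any of these.
3. **SAP 3.3.6:** on the Safety Analysis Set, report the number and percentage still on 500 mg BID at Week 24 without an AE-driven change. Report tablets taken as a percentage of the planned 24-week total, separating investigator-directed reductions from non-adherence.

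The cost is one code, a few table rows and a short edit to each document, with no added patient procedure. The SAP changes can be made before database lock. The reported tolerability may look less favourable.

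Separately, Protocol 6.6.1 ties a restart to resolution of the event (for Grade IV events and liver injury, after a DSMB judgement that it is unrelated to study drug), while Protocol 6.6.3 restarts patients whose symptoms have not resolved. The two sections must be reconciled, because they determine who reaches the reduced dose. No dosing rule is proposed here.

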8.5.1. Adverse Events

Treatment-emergent adverse events (TEAEs) are defined as AEs that worsen or commence on or after the time of start of first study drug administration. AEs, including SAEs, will be coded using MedDRA. The number and percentage of subjects experiencing TEAE, including TEAEs leading to study drug discontinuation and SAEs, will be summarized for each system organ class (SOC) and Preferred Term. In addition, AEs will be tabulated according to severity, causality, and relation to the study drug.

Individual data listings for AEs will be presented for each subject.

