3.2 Analysis Populations

3.2.1 Full Analysis Set

The Full Analysis Set consists of all subjects that meet the eligibility criteria and enroll into the study (Visit 1 Day 1).

The Full Analysis Set will be the primary population for all efficacy analyses. Only subjects with results for the specified efficacy parameter will be included in each analysis.

3.2.2 *Safety Analysis Set*

The Safety Analysis Set consists of all enrolled subjects who receive at least one dose of study drug.

The Safety Analysis Set will be the primary population for all safety analyses.

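### SAP 3.5.1: the overview's SAE row is not limited to treatment-emergent events, and the withdrawal row is worded differently from its own listing and the protocol (low severity)

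*SAP*

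**What the plan says.** SAP 3.5.1 sets a collection window that opens at consent: "All AEs regardless of seriousness or relationship to study drug, including those occurring during the Screening Period, are to be recorded". It then defines the treatment-emergent subset, with the first dose of NTZ as the dividing line: "TEAEs are defined as AEs that worsen in severity or relationship to study drug or commence on or after the time of start of first" (cut short here).

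The overview table is built on the Safety Analysis Set (SAP 3.2.2): "The Safety Analysis Set consists of all enrolled subjects who receive at least one dose of study drug". Its first two rows, any TEAE and any drug-related TEAE, are restricted to treatment-emergent events. The rows for SAEs, drug-related SAEs, deaths and withdrawals are not. The main withdrawal row reads "Any AEs leading to withdrawal from study or study drug".

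The same section describes the listings differently: "Listings will be presented specifically for SAEs and TEAEs leading to withdrawal from study or study drug". Protocol 8.5.1 plans a summary as follows: "The number and percentage of subjects experiencing TEAE, including TEAEs leading to study drug discontinuation and SAEs, will be summarized". SAP 2.1 gives the primary endpoint as "Adverse events (AEs) including treatment-emergent AEs (TEAEs) and serious AEs (SAEs), laboratory evaluations" and further safety measures. SAP section 6 states that nothing has changed from the protocol's analysis.

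**The concern.** Rows of one table cover different periods. The TEAE rows start at the first dose; the SAE row starts at consent. The gap can contain events that the trial's own procedures cause. Protocol Table 1 requires a liver biopsy in screening when none was done in the past 6 months, Protocol 6.8.1 allows it to be repeated, and Protocol 6.3 adds the deuterated-water run-in. Protocol 7.1.1 treats complications of protocol procedures as adverse events, and under 7.1.3 hospitalization makes an event serious. No criterion in Protocol 4.3 specifically bars a patient who has recovered from such a complication from being dosed.

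There is no control arm to show a background rate of such events. The SAP also specifies no count of treatment-emergent SAEs, since its tables by system organ class and preferred term cover TEAEs and drug-related TEAEs. A reader of the SAE percentage would naturally take it as the rate on NTZ, and it might not be.

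The withdrawal row raises a smaller matter of consistency: the count and the listing meant to support it are defined on different sets of events.

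**Working it through.** The plan states no figure for this point, so there is nothing to reproduce. The check has two parts: which rows can be reached by a pre-dose event, and how large the effect is.

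**Which rows are exposed**

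| Overview row | Limited to TEAEs? | Can a pre-dose event enter? |
|---|---|---|
| Any TEAE; drug-related TEAE | Yes | No, unless it worsens after dosing, when it is a TEAE by definition |
| Any SAE | No | Yes, if the patient is later dosed |
| Drug-related SAE; drug-related AE leading to withdrawal | No | In practice no. The SAP counts only possibly related and related events, and Protocol 7.2.2 requires for both a plausible time sequence from drug administration |
| Death due to an AE | No | The death itself cannot precede dosing, because the set contains only dosed patients |
| AE leading to withdrawal | No | Only if the event began before dosing, did not worsen in severity or relationship, and still led to withdrawal after at least one dose |

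For the last row, Protocol 7.2.3 also records the action taken with study drug as not applicable when the event began before treatment. A pre-dose event would thus not normally be coded as a drug withdrawal. The expected change in this row is about zero.

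**Size for the SAE row**

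Inputs:
- n = 20 (Protocol 4.1 and 8.7; SAP 2.2.4), assumed here to be the number dosed.
- Screening of up to 42 days (Protocol Table 1), treatment of 24 × 7 = 168 days, follow-up of 28 days.
- p, the risk that a dosed patient had an SAE before the first dose. The documents do not give it; 1%, 2% and 5% are assumptions.

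Steps:
1. Each patient whose only SAE was pre-dose adds 100/20 = 5.0 percentage points.
2. If that is the only SAE in the trial, the row changes from 0/20 to 1/20. Exact (Clopper-Pearson) 95% limits:
   - 0/20: upper limit 1 − 0.025^(1/20) = 16.8%, so 0% to 16.8%.
   - 1/20: lower limit 1 − 0.975^(1/20) = 0.1%; the upper limit solves (1−q)^20 + 20q(1−q)^19 = 0.025, giving q = 24.9%. So 0.1% to 24.9%.
3. The chance of at least one such patient is 1 − (1 − p)^20, and the expected number is 20p:

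| Assumed p | Chance of at least one | Expected number |
|---|---|---|
| 1% | 18.2% | 0.2 |
| 2% | 33.2% | 0.4 |
| 5% | 64.2% | 1.0 |

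4. Screening is up to 42/(42 + 168 + 28) = 42/238 = 17.6% of the scheduled time from consent to the 4-week follow-up.

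The SAP plans no confidence interval for adverse event counts, so the limits in step 2 only give a sense of scale.

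**The case against.** The strongest reply is that little is exposed and the rest is visible anyway. Patients never dosed are outside the Safety Analysis Set, so screen failures cannot enter. The drug-related rows are protected by the causality definitions in Protocol 7.2.2. The TEAE rows and the tables by system organ class and preferred term are untouched. SAEs are listed, Protocol 8.5.1 provides adverse event listings by subject, and onset dates are collected (Protocol 7.3.1). With 20 patients, anyone can pick out a screening SAE. All of this stands, and it is why the point is minor.

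The reply also has force on the protocol. A reader might infer that the SAP contradicts Protocol 8.5.1 by not restricting SAEs to treatment-emergent ones. The documents do not support that. The sentence "The number and percentage of subjects experiencing TEAE, including TEAEs leading to study drug discontinuation and SAEs" can be read with SAEs as a kind of TEAE or as a separate item. Protocol 8.5 and SAP 2.1 both name SAEs without a treatment-emergent limit, and the SAP's SAE listing is unrestricted too, so for SAEs the count and the listing agree.

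What the reply does not remove is that the only specified all-cause SAE percentage can contain events from before any NTZ was taken. A listing lets a careful reader correct the percentage, but the table would still print it uncorrected. The reply also leaves the withdrawal wording mismatched.

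**Conclusion.** The point holds in a limited form, at low severity. One descriptive row, any SAE, can include screening events in dosed patients, at 5 percentage points each. This assumes 20 dosed patients and that the patient has no SAE after dosing as well. How likely it is depends on a pre-dose SAE rate that the documents do not give. The withdrawal row is inconsistent with its own listing and with Protocol 8.5.1, contrary to the declaration in SAP section 6, with an expected numerical effect of about zero.

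A reader might go further and conclude that pre-dose events contaminate the primary safety result as a whole, or inflate withdrawals and drug-related SAEs. The documents do not support this: the Safety Analysis Set, the causality definitions and the action-taken coding close those routes in all but very narrow cases.

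**What to change.** In SAP 3.5.1:
- Count treatment-emergent SAEs in the overview, using the same TEAE flag as the first two rows.
- Show SAEs with onset before the first dose in a separate row or listing, so that nothing is lost. State how an SAE that starts before dosing and worsens afterwards is shown; under the existing definition it is treatment-emergent.
- Word the withdrawal row as TEAEs leading to withdrawal, to match the listing and Protocol 8.5.1. The declaration in SAP section 6 then holds on this point.

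The drug-related rows need no change on numerical grounds.

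The cost is a few words in the SAP and one extra row or listing. The TEAE flag is already defined, data collection does not change, and the SAP is due to be finalized before database lock.
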